4.3.5.4. Data handling and monitoring

The three clinical study centres will jointly design the case report forms (CRF) and other data collection forms (e.g., information related to study visits, such as contact details, bookings etc) for the 2D-BioPAD clinical pilot

²⁵ Huber H., et al. Biomarkers of Alzheimer's disease and neurodegeneration in dried blood spots-A new collection method for remote settings. *Alzheimers Dement.* 2024 Apr;20(4):2340-2352. doi: 10.1002/alz.13697

²⁶ Therriault, J., et al. Comparison of Two Plasma P-Tau217 Assays to Detect and Monitor Alzheimer's Pathology. Available at SSRN: <https://ssrn.com/abstract=4572850> or <http://dx.doi.org/10.2139/ssrn.4572850>

²⁷ Hirtz, C., et al. Comparison of ultrasensitive and mass spectrometry quantification of blood-based amyloid biomarkers for Alzheimer's disease diagnosis in a memory clinic cohort. *Alz Res Therapy* 15, 34 (2023). <https://doi.org/10.1186/s13195-023-01188-8>

²⁸ Janelidze S., et al. Head-to-Head Comparison of 8 Plasma Amyloid- β 42/40 Assays in Alzheimer Disease. *JAMA Neurol.* 2021;78(11):1375-1382. doi:10.1001/jamaneurol.2021.3180

study. Investigators at all clinical study centres will file all data per subject. An explanation for the omission of any required data should appear on the appropriate CRF section. All data recorded in the CRF will be signed off by the study centre PI or their appropriate designee.

Data from CRFs will be entered in a web-based database, e.g., via REDCap (Research Electronic Data Capture), a secure web application for building and managing online surveys and databases (already available at UEF), by trained personnel at each clinical study centre. All changes made following initial submission of data will have an electronic audit trail with a date. Specific instructions and further details will be outlined in the study manual of operations. The PI at each centre will monitor the study at their own centre to ensure quality and integrity of data collected. They will review study files, ethical/regulatory documents, consent forms and allocate adequate time for other study monitoring activities. Each PI must permit study-related monitoring visits, audits, review by the relevant authorities, and allow direct access to source data and source documents provided that subject confidentiality is protected.

Source documents (paper or electronic) are those in which research participant data are recorded and documented for the first time. Source data will be collected in Finnish (UEF), Greek (GAARDR), or German (ZI). Source documents in paper format will be kept in a locked location at each study centre, to which only authorized people involved in the study will have access. Each clinical study centre must maintain adequate source documentation to allow reliable verification and validation of the study data.

CRFs, other data collection forms, manual of operations, and the web-based database will be ready before the start of the study (M24).

4.3.5.5. *Safety evaluations*

Due to the design of this study, HCPs and patients will not have access to AD plasma biomarker results from the 2D-BioPAD diagnostic aid during the diagnostic workup of a patient, i.e., there is no risk of interference with diagnostic, treatment, and care decisions, which will be made according to established standard procedures at each study centre.

Blood sampling is overall safe and well tolerated, and participation in this study is expected to have a low risk of adverse events. Blood sample collection may cause discomfort, mild bruising, and/or bleeding where the needle is inserted. Some people may become dizzy, lightheaded, or feel faint. Infections rarely occur. For efficient collection of safety information relevant to the 2D-BioPAD study participation, we will collect and evaluate data regarding (serious) adverse events that occur according to the following pre-specified conditions:

- During blood sampling for the 2D-BioPAD clinical pilot study and/or afterwards for the duration of the 2D-BioPAD study visit
- Involving the puncture site used for blood sampling.

Definitions

Adverse Event (AE): any untoward occurrence in a participant.

Serious Adverse Event (SAE): any untoward and unexpected occurrence or effect that:

- Results in death
- Is life-threatening – refers to an event in which the participant was at risk of death at the time of the event; it does not refer to an event which hypothetically might have caused death if it were more severe
- Requires hospitalisation
- Results in persistent or significant disability or incapacity

Medical judgement will be exercised in deciding whether an AE is serious and/or severe in all situations. Important AEs that are not immediately life-threatening or do not result in death or hospitalisation but may jeopardise the participant or may require intervention to prevent one of the other outcomes listed in the definition above, will also be considered serious.

Reporting Procedures

Following the signing the informed consent, any events that are reported by the participant or observed by study team members, and meet the abovementioned pre-specified conditions, will be reported as AE or SAE, depending on which criteria are being met. Depending on the nature of the event the reporting procedures below will be followed. Any questions concerning (S)AE reporting will be directed to the Principal Investigators in the first instance. (S)AEs will be recorded by participant study ID numbers. No identifiable information in relation to any (S)AEs reported will be disclosed outside of the relevant study centre.

A Serious Adverse Event (SAE) form will be completed and emailed to the Principal Investigators within 24 hours. Study centre investigators will report any SAEs as required by their local regulations (e.g., to their Ethics Committee or other relevant regulatory authorities).

Causality

The assignment of causality for AEs and SAEs will be made by the trial Principal Investigators as follows:

- *Unrelated*: No evidence of any causal relationship
- *Unlikely*: There is little evidence to suggest there is a causal relationship (e.g., the event did not follow a reasonable temporal sequence after administration of the study procedure or did not follow a known or expected response pattern to the suspected procedure). There is another reasonable explanation for the event (e.g., the patient's clinical condition, other concomitant procedure, or treatment).
- *Possible*: There is some evidence to suggest a causal relationship (e.g., because the event followed a reasonable temporal sequence after administration of the study procedure or followed a known or expected response pattern to the suspected procedure). However, the influence of other factors may have contributed to the event (e.g., the patient's clinical condition, other concomitant procedures, or treatments).
- *Probable*: There is evidence to suggest a causal relationship and the influence of other factors is unlikely.
- *Definite*: There is clear evidence to suggest a causal relationship and other possible contributing factors can be ruled out.

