4.3.1. Selection criteria

Table 5. Inclusion and exclusion criteria for the prospective study

Inclusion criteria	
Patients	
 • Age 50 years or older • Subjective cognitive complaints, MCI or dementia diagnosis, as per centre-specific standard assessment procedures • Ongoing assessment after first referral to the clinical study centre, or diagnostic procedures completed \leq3 months before the first 2D-BioPAD study visit • Ability to provide written informed consent
HCPs	
 • 18 years or older • Certified HCP (e.g., nurse, physician) • Actively involved in the centre-specific assessment process for dementia-related diseases
Exclusion criteria	
Patients	
 • Any health conditions that substantially affect communication and/or ability to participate in study procedures, as judged by the study nurse or physician • Impaired capacity to consent as per centre-specific standard assessment

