4.3.2. Overall study design

This is a **multicentre prospective observational study**. HCPs will use the 2D-BioPAD diagnostic aid to measure AD blood biomarkers in individuals referred to the three study centres for assessment of suspected AD/dementia disease. 2D-BioPAD baseline visit activities will be conducted only after the informed consent form has been signed. The overall study design is summarised in Figure 4.

The 2D-BioPAD baseline visit will be conducted after centre-specific standard assessment procedures are completed and a diagnosis and treatment/care plan have been decided according to standard clinic procedures. The 2D-BioPAD baseline visit can be a separate visit or can be conducted at the end of an already scheduled standard clinic visit, depending on patient preference and study centre logistics. The aim is to reduce burden for patients and limit interference with routine clinical activities.

As validation of the biomarker measures from the 2D-BioPAD diagnostic aid will be done as part of this study, these biomarker results will not be used for diagnosis or to guide treatment plans. HCPs participating in the 2D-BioPAD clinical pilot study who are directly involved in the standard diagnostic work-up and decision-making for patients tested with the 2D-BioPAD diagnostic aid must not have access to the biomarker results before the diagnosis and treatment/care plan are decided (See also Section 4.1.5.1 Ethical aspects).

[figure not shown]

Figure 4. 2D-BioPAD clinical pilot study design for the prospective stage

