* State-of-the-art CSF biomarkers as described in section 4.1.4.1. To reduce patient burden, the 2D-BioPAD prospective study will use CSF biomarker values where available from standard assessment procedures at the clinical study centres.

** Benchmarking equipment for plasma AD biomarkers as described in Section 4.1.4. All plasma samples for all patients will be analysed at the UEF Brain Research Unit biomarker laboratory.

Data collected from HCPs will include:

- Age
- Gender (self-reported)
- HCP group (e.g., nurse, physician)
- Clinical specialty
- Years and degree of experience (e.g., resident, specialist)
- Questionnaire including feedback about experience with the diagnostic aid and biomarker results on the 2D-BioPAD digital interface, acceptability, trust and satisfaction (short questions with Likert-scale answers to be answered via the digital interface after blood sampling and visualisation of plasma biomarker results for each patient; longer questionnaire to be answered e.g., 3-4 times during the study after the HCP has conducted blood sampling and visualisation of plasma biomarker results for multiple patients).

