4.3.4.3. At follow-up

For all 300 patients, up to 1 year follow-up after baseline will be included if the diagnosis is unclear at baseline and follow-up is scheduled as per centre-specific standard procedures. The following patient-related data will be collected:

- Cognitive status
 - Control / no dementia disease / subjective cognitive complaints
 - MCI
 - Dementia type
- Date of diagnosis

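### For patients undiagnosed at baseline, HCPs can see the 2D-BioPAD result before the reference diagnosis is made, so the no-interference statement in 4.3.5.5 is unsupported for them

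*Protocol*

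**What the plan says.** Section 4.3.5.5 (Safety evaluations) makes an unconditional statement: "HCPs and patients will not have access to AD plasma biomarker results from the 2D-BioPAD diagnostic aid during the diagnostic workup of a patient". It infers that decisions on diagnosis and care cannot be disturbed.

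That inference rests on section 4.3.2, which sets the order of events: "The 2D-BioPAD baseline visit will be conducted after centre-specific standard assessment procedures are completed and a diagnosis and treatment/care plan have been decided". The same section provides that participating HCPs directly involved in a patient's work-up and decisions "must not have access to the biomarker results before the diagnosis and treatment/care plan are decided". Sections 4.1.5.1 and 4.3.2 add that device results are not to be used for diagnosis or care.

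Section 4.3.4.1 has HCPs look at the results patient by patient. Their feedback consists of "short questions with Likert-scale answers to be answered via the digital interface after blood sampling and visualisation of plasma biomarker results for each patient". Section 4.3.4.2 repeats this for the first 30 patients. By Table 5 these HCPs must be "Actively involved in the centre-specific assessment process for dementia-related diseases".

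Patients without a clear diagnosis are included on purpose. Section 4.3.4.3 says that "up to 1 year follow-up after baseline will be included if the diagnosis is unclear at baseline", and that cognitive status, dementia type and date of diagnosis are then recorded. Section 4.1.3 says that these diagnoses come from routine assessments and that less clear-cut cases go to consensus. In Table 9 the primary accuracy outcome takes the centre's clinical AD diagnosis as reference. Section 4.4.3 gives noninferiority to the benchmark as the main hypothesis.

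**The concern.** In a diagnostic accuracy study the reference standard should be set without knowledge of the index test. The protocol achieves this by timing: diagnosis first, device second. The timing works for patients diagnosed before the baseline visit. It does not work for patients who leave that visit undiagnosed, because the device result is on the screen while their work-up is still open.

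If someone who has seen the result then takes part in the follow-up or consensus diagnosis, the device can influence the label it is judged against. This would happen in the patients who are hardest to classify. The device's full panel is displayed on site, whereas the benchmark is measured at the UEF laboratory and may inform diagnosis only where it is already standard care. Any leak would therefore probably help the device in the comparison on which the main hypothesis rests. Once a result has been seen, no later analysis can restore the masking.

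**Working it through.** **Setting the sections side by side**

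1. The mask in 4.3.2 lasts until the diagnosis is decided, and 4.3.2 treats that as done before the baseline visit.
2. Sections 4.3.3.2, 4.3.4 and 4.3.4.3 describe patients for whom it is not done by then.
3. Section 4.3.4.1 makes no exception for these patients when HCPs view and rate results.
4. Read strictly, 4.3.2 keeps directly involved HCPs masked for up to a year in these patients, but no procedure carries this out (no flag, no assignment of another HCP, no delayed display). Read loosely, a provisional baseline conclusion lifts the mask.
5. Under either reading, the unconditional statement in 4.3.5.5 is not secured for this subset.

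**Illustration of size**

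The protocol gives no figure on this point, so there is nothing to reproduce. It does not state the share of unclear patients, the influence of a seen result, the AD prevalence or the accuracy of either test. All of these are assumed; only N = 300 is from the document.

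- f = share inconclusive at baseline: 10%, 20%, 30% (30, 60, 90 of 300)
- q = probability that the final label in such a patient follows the device result rather than the true state: 0 to 0.50
- p = AD prevalence: 0.40 or 0.50
- Device and benchmark both have true sensitivity (Se) and specificity (Sp) of 0.80, with errors independent given the true state

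Let w = f·q and let P_T = p·Se + (1−p)(1−Sp) be the device-positive rate.

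- P(reference positive) = (1−w)p + w·P_T
- Apparent device sensitivity = [(1−w)p·Se + w·P_T] / P(reference positive)
- Apparent benchmark sensitivity = [(1−w)p·Se + w(p·Se² + (1−p)(1−Sp)²)] / P(reference positive)

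Largest case (f = 0.30, q = 0.50, p = 0.40):

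- w = 0.15 and P_T = 0.32 + 0.12 = 0.44
- P(reference positive) = 0.340 + 0.066 = 0.406
- Device: (0.272 + 0.066)/0.406 = 0.833
- Benchmark: (0.272 + 0.15 × 0.28)/0.406 = 0.314/0.406 = 0.773
- Difference: 5.9 points, when the true difference is zero

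Spurious sensitivity advantage of the device, in percentage points (p = 0.40 / p = 0.50):

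| f | q = 0 | q = 0.10 | q = 0.25 | q = 0.50 |
|---|---|---|---|---|
| 10% | 0 / 0 | 0.4 / 0.3 | 1.0 / 0.8 | 2.0 / 1.6 |
| 20% | 0 / 0 | 0.8 / 0.6 | 2.0 / 1.6 | 4.0 / 3.2 |
| 30% | 0 / 0 | 1.2 / 1.0 | 3.0 / 2.4 | 5.9 / 4.8 |

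The gap arises because the device's apparent sensitivity rises and the benchmark's falls. It depends on the independence assumption: if the two tests always agreed, the gap would be zero.

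**The case against.** The protocol has safeguards, and they count. The ban on using device results in 4.1.5.1 has no end date, so it covers follow-up. The bar in 4.3.2 is tied to the diagnosis rather than to the visit, so on a literal reading it still protects an undiagnosed patient. These points make influence less likely. They do not amount to masking, because someone told not to use a result has still seen it, and the bar has no procedure behind it for unresolved patients.

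Four stronger readings are tempting, and the document does not support them.

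- *The masking rule and the per-patient questionnaire cannot both hold.* They can. Table 5 requires activity in the centre's assessment process, not in every patient's diagnosis, and section 4.3 provides for at least two HCPs per centre. An HCP with no part in that patient's diagnosis could run the device and rate the result. What is missing is a provision for this.
- *Only the device can gain.* Section 4.1.3 says plasma NfL is already routine in Finland, and 4.1.5.1 lets such results inform diagnosis where they are standard. Device and benchmark also measure the same analytes, so a label moved towards the device moves the benchmark's apparent accuracy too. A net advantage to the device is probable, not certain.
- *The follow-up diagnosis is the primary reference.* The text implies this, since follow-up collects little except diagnostic status, but does not say it. If the baseline label were used, or unclear cases were analysed apart, this route into the primary outcome would close.
- *Everyone recruited during assessment is affected.* Table 5 does admit patients under "Ongoing assessment after first referral to the clinical study centre", but 4.3.2 still places the baseline visit after their diagnosis. The exposed group is those unclear at that visit.

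It is also fair to say that this is a pilot meant to give preliminary information, and that 4.3.5.1 foresees limiting unclear cases if there are delays.

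**Conclusion.** The point holds in a limited form. For patients undiagnosed at baseline, the protocol lets HCPs from the centre's assessment process see the device result before a diagnosis that may become the primary reference standard. Nothing in the procedures keeps that diagnosis masked, so the statement of no interference in 4.3.5.5 needs correcting for them.

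The bias is possible, not established. It is confined to a subset whose size is not given, and it probably favours the device. The range of 0 to about 6 points in sensitivity difference rests wholly on the assumed inputs above and shows scale only; it is zero if seen results have no influence. Analyses referenced to CSF or to benchmark plasma are not affected, because those references are laboratory measurements.

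This is a matter of conduct, so it needs to be settled in the protocol before results are viewed.

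**What to change.** - In 4.3.2, define the release point for HCPs involved in a patient's diagnosis as the locking of the final study diagnosis: the baseline diagnosis, or the follow-up diagnosis where baseline is inconclusive.
- Flag patients as inconclusive on the CRF before the device is run. For them, either have the device run and its result viewed by an HCP at the centre who takes no part in that patient's diagnosis, including any consensus discussion, or have the app withhold the result and the result-related questions until the diagnosis is locked.
- Reword 4.3.5.5 to match, and make 4.3.4.1 and 4.3.4.2 consistent with it.
- Add a sensitivity analysis of the primary accuracy outcome restricted to diagnoses fixed before device testing. It leaves out the hardest cases, so it should accompany the main analysis and not replace it.

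The cost is one CRF flag and either a staffing rule or an app display setting. No extra staff are needed, given at least two HCPs per centre. The downside is that result-viewing feedback for inconclusive patients comes from a different HCP or, with withholding, arrives up to a year later. HCP experience is itself a primary outcome, so the uninvolved-HCP option disturbs the study less. Neither option changes patient care.

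### The SAE definition makes seriousness depend on an event being unexpected, so a foreseen blood-sampling reaction that leads to hospital admission may be reported only as an AE

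*Protocol*

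**What the plan says.** All the relevant text is in Protocol section 4.3.5.5, Safety evaluations.

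- **Foreseen reactions.** "Blood sample collection may cause discomfort, mild bruising, and/or bleeding where the needle is inserted". The text continues: "Some people may become dizzy, lightheaded, or feel faint. Infections rarely occur".
- **AE.** "Adverse Event (AE): any untoward occurrence in a participant". Expectedness plays no part.
- **SAE.** Defined as "any untoward and unexpected occurrence or effect that" has one of four outcomes. One of these is "Requires hospitalisation".
- **Second route to serious.** "Important AEs that are not immediately life-threatening or do not result in death or hospitalisation" are also serious if they may put the participant in jeopardy, or may need intervention to prevent another of the listed outcomes. This route carries no expectedness condition.
- **Judgement.** A preceding sentence leaves the decision on seriousness to medical judgement in every situation.
- **Reporting.** Events in scope are classed as AE or SAE according to the criteria they meet. "A Serious Adverse Event (SAE) form will be completed and emailed to the Principal Investigators within 24 hours". Onward reporting to ethics committees or authorities is likewise stated for SAEs; no deadline is given for other AEs.

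**The concern.** Seriousness describes the outcome of an event; expectedness describes whether it was foreseen. The definition joins the two with 'and', so a foreseen event does not meet it whatever its outcome.

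This matters here because collection is deliberately narrow. Only events during sampling or the rest of the visit, or events involving the puncture site, are collected. Much of what falls in that window is of the kind the protocol itself foresees. The causality scale also counts a known or anticipated response pattern towards relatedness. The condition therefore tends to bear on the events most likely to be caused by the study procedure.

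At stake are the SAE label, the 24-hour form and onward reporting. A summary stating that no SAEs occurred could be formally correct and still mislead.

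**Working it through.** No figure in the protocol is in question and no arithmetic applies. The check is to pass test cases through the clauses of section 4.3.5.5. All are assumed to fall within the collection window and so to be AEs.

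| Case | Main SAE definition | Important-AE clause | Reported as |
|---|---|---|---|
| A. Foreseen reaction, no admission, judged to jeopardise the participant | Not met: no listed outcome, and not unexpected | Met | SAE |
| B. Same reaction, admission required | Outcome met, unexpectedness not met | Natural reading: not met. Literal 'or': met if not immediately life-threatening | AE or SAE, depending on the reading |
| C. Unforeseen reaction, admission required | Met | Not needed | SAE |

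**A against B.** On the natural reading the order is inverted: the worse outcome receives the lower classification.

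**Why that reading is the natural one.** The important-AE clause adds to the list, as its *also* shows. Its intervention limb concerns preventing another of the listed outcomes. It is therefore aimed at events that have not reached one.

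**The literal alternative.** The clause says not immediately life-threatening *or* not resulting in death or hospitalisation. Taken word by word, an admitted event that is not immediately life-threatening satisfies the first limb and is serious if it may jeopardise the participant. Two problems remain. The unexpectedness condition would then have little effect for such admissions, so the two clauses would pull against each other. And a foreseen reaction that is both immediately life-threatening and leads to admission satisfies neither limb.

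**B against C.** The difference rests on whether the reaction was expected. The protocol defines no such term and does not designate its list of sampling reactions as the reference for it.

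**Consequence for B on the natural reading.** The event is recorded as an AE and given a causality category, but neither the 24-hour form nor SAE onward reporting is triggered.

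**The case against.** There are four serious counter-arguments.

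1. **The listed reactions are mild.** The section speaks of feeling faint, not of fainting with a fall, and says only that infection is rare. An investigator could fairly call an admission after a blood draw unexpected in nature or severity, which makes it an SAE. This stands as a possible reading. Without a definition of expectedness, however, it is one investigator's choice.
2. **The 'or' in the important-AE clause.** Read literally, it catches many admitted cases. This also stands in part, with the limits shown in the working.
3. **Medical judgement.** That sentence applies to AEs, which carry no expectedness condition, so it offers a real route to the SAE label. But it does not waive the word *unexpected*, and the reporting rule still turns on which criteria are met. Three centres in three countries could classify the same event differently.
4. **Small consequence.** The section expects a low risk of adverse events, and every event in scope is still recorded and assessed for causality. This is correct and limits the weight of the point.

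A reader might infer that a foreseen reaction with admission is certainly caught by neither clause, so that no such event could be an SAE. The first three arguments show that the text does not establish this. A reader might also want to attach a probability to such an event occurring. The protocol gives no rate, so any figure would rest wholly on an assumed one.

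**Conclusion.** The point holds as a drafting defect in the safety rules. Nothing in the protocol removes the unexpectedness condition. On the natural reading, a foreseen sampling reaction that requires admission fails the main definition and is not clearly caught by the second clause. The routes that may rescue it depend on each centre's interpretation.

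The effect is confined to the SAE label, the 24-hour form and onward reporting. The number of affected events is likely small but cannot be estimated from the document. No outcome in Tables 8 and 9 and no analysis in section 4.4.3 changes. The conclusion assumes that the reactions named in the section would be treated as expected, which the protocol implies but does not state. It is worth correcting because the remedy is simple and the condition falls on the foreseeable harms of the study procedure.

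**What to change.** - Delete *and unexpected* from the SAE definition, so that seriousness depends only on the listed outcomes.
- Reword the important-AE clause so that it plainly adds events that have not reached a listed outcome, and resolve the ambiguous 'or'.
- Record expectedness as a separate field beside causality on the SAE form, and state which list serves as the reference for it.

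The cost is a short wording change in the protocol and one field on the form, with no analytical downside. The timing is favourable: a regulatory-compliant protocol is still being prepared (section 4.1.5.2) and the data collection forms are due by M24 (section 4.3.5.4). Two ethics committees have already approved version 1 (section 4.1.5.1). If the change counts as substantial it needs their approval, and it can go to them with that updated protocol.
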